Clinically, individuals with CBSDH exhibit a dramatic predisposition for thrombosis. Time-to-event graphs generated from data compiled from 629 untreated individuals show the risk of suffering a thromboembolic event is 25% by age 16 and 50% by age 29 (Mudd et al 1985). Of the events reported, 31% were cerebrovascular accidents, 51% were peripheral vein thrombosis with roughly one fourth of these involving pulmonary embolism, 4 % produced myocardial infarctions, 11% affected peripheral arteries, and 2% fell into none of these categories. These thromboembolic events constitute the major cause of morbidity and mortality in this disease (Schriver et al, 2001). In addition to the propensity toward clotting, individuals with CBSDH frequently incur cognitive impairment and exhibit a range of connective tissue disorders including markedly increased risk for ectopia lentis, marfanoid skeletal abnormalities, and osteoporosis. Incidence of CBSDH varies significantly in different populations with a recent estimate in Europe of 1 in 20,000.

There is a functional trichotomy in the nature of pathogenic mutations in CBSDH. One group of mutations is classified as “pyridoxine-responsive” as CBS enzyme function can be restored by high dose pyridoxine therapy. Such treatment effectively mitigates the biochemical and clinical findings in these individuals. The second group of functional mutations is represented by the “c-terminal CBS mutants” that are defective in their ability to respond to post-translational up-regulation by S-adenosylmethionine. Patients with this class of mutations lack mental retardation and connective tissue aspects of the phenotype and are detected after investigation of plasma Hcy levels following an idiopathic thrombotic event before the age of 40 (Maclean et al., 2004). The final group of CBSDH mutations is “classical homocystinuria” which represents the severest form of the disease.

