a. Recent cardiovascular event. Cardiovascular events (stroke, myocardial infarct, deep vein thrombosis, pulmonary embolus or thrombosis) may interfere with platelet function studies and with various mediators during the first months after the event. Patients who had such an event within the last 6 months will be excluded.

b. Patients with uncontrolled hypertension. This will remove a confounding factor from analysis of the endothelial flow studies and increase safety. 8. Informed consent: Individuals who are unwilling or unable to consent, or in the case of minors who are unwilling or unable to assent will be excluded due to lack of ability to ensure informed consent.

9. Study compliance and integrity: Individual who anticipate an inability to comply with study procedures and requirements will be excluded.

10. Hypertriglyceridemia. Individuals with a triglyceride level above 300 mg/dl will be excluded from the study. An associated increase in triglyceride levels with administration of taurine has been reported (as has a decrease in triglycerides) Exclusion of individuals who have a history of hypertriglyceridemia will decrease the likelihood that a study related increase in serum triglycerides would result in health care risks. This is a conservative approach as acute health care risk is generally seen in the setting of triglycerides > 1000 mg/dl. Historic triglyceride levels (within 5 years of the date of consent) can be used to assess eligibility. This lacking, triglycerides can be obtained as part of the study and assessed prior to administration of taurine.

F. Planned Enrollment: Enter # of Subjects in the Table Below: review the numbers for 12 and women = male (given your statement in 7A inclusion of women)

Ethnic Categories	Gender		
	Females	Males	Total
Hispanic or Latino	2	2	4
Not Hispanic or Latino	8	8	16
Ethnic Categories: Total of All Subjects	10	10	20
Racial Categories			
American Indian/Alaska Native	0	0	0
Asian	1	0	1
Native Hawaiian or Other Pacific Islander	0	0	0
Black or African American	1	2	3
White	8	8	16

Racial Categories: Total of All Subjects*	10	10	20
--	-----------	-----------	-----------

*The "Ethnic Categories Total of All Subjects" **must be equal to** the "Racial Categories Total of All Subjects"

Data listed here **reflects US population demographics and is an estimate..**

G. Study Design Details:

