Special Care Clinic
[name]
[name]

[name]
[contact]
[name]

[name] (alternate)
[contact]
[name]

Unanticipated problem or events, especially problems or events that are possibly or probably related to the study or research procedures will also be looked for. This includes monitoring for serious adverse events (SAEs) since such an event is not anticipated. In an event of an SAE, the monitoring PI will discuss the event with one of the co-investigator MDs within 24 hours of knowledge of the event to allow for decisions regarding the data and the safety to all participants. All unanticipated problems and unanticipated events will also be discussed with one of the co-investigating MDs within five working days of knowledge of the problem or event. Any identified trend in AEs will also be discussed within five working days of knowledge of the trend with one of the co-investigator MDs. Of note, the minimal risk for adverse events relative to taurine intake, the low number of participants (N=16 with drug exposure) and short duration of the study (5 days) make it very unlikely that any AE trend would be detected much before the end of the study.

There are no conflicts of interest for the PI or the co-investigator MDs responsible for data safety management.

B. Describe SAEs and AEs for this protocol and the SAE/AE reporting plan:

Events that result in death, immediate hospitalization, or prolonged hospitalization to prevent death or serious disability will be considered SAEs. Any other untoward medical occurrence temporally associated with the study will be considered AE. This includes headaches, gastrointestinal discomfort, and other events captured on the adverse event/compliance sheet that are without significant health risk and/or are potentially unrelated to study. Clinically significant changes in blood pressure or safety monitoring labs will be considered an AE. Specifically, liver function results that exceed two times the upper limit of normal, triglycerides greater than 400 mg/dl, and/or hypotension, with a blood pressure <90mmHg in adults or <the 5th percentile for age in children after taurine supplementation, will

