be considered an adverse event in the setting of normal subject values prior to taurine supplementation. Any intercurrent illness or injury that represents an exacerbation of pre-existing condition (e.g., increase frequency or severity) will also be considered an AE. In such cases it will be preferred to record the diagnosis as the AE rather than a series of terms relating to the diagnosis (e.g., worsening of asthma). An adverse drug reaction will be all noxious and unintended responses to taurine product. This means that a causal relationship between taurine and an AE is at least a reasonable possibility (i.e., the relationship cannot be ruled out).

The PI and one of the co-investigating MDs will determine the severity of the event and if the SAE or AE is related to the protocol using the categories noted below. Review of their determination will be sought from the Safety Officers. In the case of deferring opinions, higher grade of severity the more related rating will be accepted

Grade	Description
Mild	No limitation of usual activities
Moderate	Some limitation of usual activities
Severe	Inability to carry out activities

Not Related	The adverse finding was present prior to exposure to the investigational product, having the same or milder intensity OR The finding is considered likely to be related to an etiology other than the investigational product, that is, there is no evidence or arguments to suggest a causal relationship to the investigational product.
Possibly related	Exposure to investigational product and onset of the finding are reasonably related in time AND The adverse finding could be reasonably be explained by factors or causes other than exposure to investigational product.
Probably related	Exposure to investigational product and onset of the finding are reasonably related in time AND The adverse finding is more likely explained by exposure to investigational product than by other factors or causes.

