SAEs will be reported to one of the co-investigator MDs as well as the Safety Officers, FDA, COMIRB, the CTRC within five working days of knowledge of the event. The participant's PCP will also be notified if deemed appropriate by the co-investigator MD. Unanticipated problems or events that result in an actual unforeseen harmful or unfavorable occurrence to the subject or others with also be reported to one of the co-investigating MDs within five working days of knowledge of the event. Information that indicates a change to the risks or benefits of the study will also be reported within five days of discovery to the Safety Officers,

FDA, COMIRB and CTRC. No new patients will be enrolled or studied until the SAE has been reviewed and appropriate action taken by the above listed bodies.

The PI will notify co-investigator MDs of abnormal safety monitoring lab results within five working days of resulted values. If deemed clinically appropriate by co-investigator MD, the subjects PCP will be notified. All other AEs will be logged and reported to COMIRB yearly or at the time of continuing review.

For full list of events to be reported to COMIRB see the Reportable Event Sheet to be used for monitoring and tracking individual events attached in Appendix V - Supplemental Materials.

A summary of data monitoring and reporting flow during the active portion of the study is noted below. A flow diagram of this information can be found in Appendix V - Supplemental Materials in the CTRC protocol application.

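### The SAE definition omits life-threatening, disabling and medically important events, so such an event managed without admission triggers no SAE safeguard and is expedited only if judged unanticipated or risk-changing

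*Combined protocol and SAP*

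**What the plan says.** Section 8.B defines seriousness in one sentence: "Events that result in death, immediate hospitalization, or prolonged hospitalization to prevent death or serious disability will be considered SAEs". The next sentence sets the default class: "Any other untoward medical occurrence temporally associated with the study will be considered AE". The same section also places in the AE class "Any intercurrent illness or injury that represents an exacerbation of pre-existing condition".

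Severity is graded separately. The top grade, Severe, is described as "Inability to carry out activities". No rule links that grade to SAE status or to a reporting deadline.

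Several consequences follow from SAE status. Section 8.A says: "In an event of an SAE, the monitoring PI will discuss the event with one of the co-investigator MDs within 24 hours of knowledge". Sections 8.A to 8.C add an expedited report, a Safety Officer meeting, a hold on new patients, and discontinuation or suspension. For what remains, section 8.B says: "All other AEs will be logged and reported to COMIRB yearly or at the time of continuing review".

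On the disease itself, section 3 describes thromboembolism as the leading source of illness and death. Of the reported events, "51% were peripheral vein thrombosis with roughly one fourth of these involving pulmonary embolism".

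**The concern.** The definition turns on death or hospital admission. Disability appears only as something that a hospital stay is meant to prevent, not as an outcome that makes an event serious. Threat to life and medical importance do not appear at all. The classification therefore depends on where an event was managed rather than on what it was.

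That matters in this population. A deep vein thrombosis during or shortly after taurine is an event that the Safety Officers would be expected to consider promptly. If the subject is not admitted, the plan makes it an AE, and the machinery for prompt independent review does not start. In a pilot with up to 16 exposed subjects, including children from age 8, a single such event could be the main safety information that the study yields.

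**Working it through.** No power or error-rate figure bears on this point, so the check is a trace through the text, followed by a rough scale.

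**Step 1: what needs SAE status.** Take a non-fatal event managed without admission.

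- Discussion with a co-investigator physician within 24 hours (8.A): SAE only.
- Report within five working days to the Safety Officers, FDA, COMIRB and CTRC (8.B): SAE only.
- Safety Officer meeting within one week (8.A, 8.B): SAE only.
- Hold on enrolling or studying new patients (8.B): SAE only.
- Subject discontinuation and protocol suspension (8.C): an SAE possibly related to the protocol.

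All five require SAE status, so the event triggers none. The other stopping criteria in 8.C concern liver tests, triglycerides, hypotension or safety laboratory changes in two or more subjects. A clinical thrombosis meets none of these by itself, however many subjects have one.

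**Step 2: what remains without SAE status.**

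- Unanticipated harmful events go to a co-investigator physician within five working days (8.A, 8.B). No other recipient is named.
- Information that changes the risks goes to the Safety Officers, FDA, COMIRB and CTRC within five days (8.B). Someone must first judge that the event changes the risks.
- The Reportable Event Sheet (supplementary materials) records unforeseen harmful events, related or not, for COMIRB. It gives no deadline.
- AEs are reviewed within five working days of each subject's completion (8.A, 8.B). The follow-up call comes one to two weeks after completion (footnote to the visit schedule), so an event first reported there could arrive after that review.
- Safety Officers review the severity and relatedness ratings of AEs as well as SAEs (8.B), with no deadline stated for that review.
- AE trends are discussed within five working days (8.A, 8.B). Section 8.A itself considers it very unlikely that a trend would be detected much before study end.

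None of these routes states an automatic hold. Thrombosis is also a known complication of the disease (section 3). It can therefore be read as foreseen, or as a worsening of a pre-existing condition, which 8.B classes as an AE.

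**Step 3: scale.** Inputs from section 3: untreated thromboembolic risk of 25% by age 16 and 50% by age 29. Input from 8.A: 16 exposed subjects. Assumption: constant hazard within each age span.

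- Birth to 16: -ln(0.75)/16 = 0.0180 per person-year.
- Ages 16 to 29: ln(0.75/0.50)/13 = 0.0312 per person-year.
- Over 5 days: 16 × 5/365.25 = 0.219 person-years, giving 0.0039 to 0.0068 expected events.
- Over 20 days (assumed: six study days plus two weeks to the call): 16 × 20/365.25 = 0.876 person-years, giving 0.0158 to 0.0273 expected events.

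These rates come from untreated patients and ignore the exclusion of anyone with an event in the last 6 months. They show order of magnitude only.

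**The case against.** The strongest reply is that the plan has other routes and that the event is improbable. Both parts are true. A reader might infer that an outpatient thrombosis would be reported only once a year, or would slip past every safeguard. The documents do not support that. The yearly rule covers what is left after the faster routes in step 2, and compiled safety reviews also take place before the dose increase and before children are recruited. The flow diagram of the monitoring plan was not available for this check, so no statement about every safeguard could be made in any case. What stands against the reply is that these routes rest on a judgement, reach fewer people or lack a deadline, and none imposes a hold.

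Three further inferences are tempting and should not be drawn.

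- From section 3, 0.51 × 0.75 = 0.38 of events were peripheral vein thrombosis without pulmonary embolism. This does not measure the gap, because the documents do not say how often such events are managed without admission.
- Exclusion 7a bars entry for 6 months after a thrombosis, which might look like a safety judgement. Its stated reason is measurement: "Cardiovascular events (stroke, myocardial infarct, deep vein thrombosis, pulmonary embolus or thrombosis) may interfere with platelet function studies".
- Taurine is studied partly for its effect on coagulation, but the mouse data in section 4 point towards less clotting. The documents do not predict harm in this direction.

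The scale in step 3 limits how often the gap would matter. It does not justify the definition, because expedited review exists for rare grave events.

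**Conclusion.** The point holds in a limited form. The SAE sentence leaves out three kinds of event, and the default rule then classes them as AEs when they are non-fatal and managed without admission. This is a stated rule that misclassifies events, not a detail left unwritten. Five of five SAE-specific safeguards are lost for such an event, and expedited reporting depends on its being judged unanticipated or risk-changing.

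The gap is bounded. Any such event that leads to immediate admission is already an SAE, and the expected number of thromboembolic events over the study is well below one (about 0.004 to 0.027 under the stated assumptions). The conclusion rests on the text of section 8 and the Reportable Event Sheet; the rate calculation does not carry it. It merits correction because it concerns participant safety and the correction is cheap.

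**What to change.** Extend the SAE sentence in section 8.B to include life-threatening events, persistent or significant disability, and other medically important events, whether or not the subject is hospitalised. The purpose is seriousness classification and expedited reporting: these events should enter the five-working-day report and Safety Officer review.

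The sponsor should then reconcile the rest of 8.A to 8.C and the Reportable Event Sheet with that definition. This includes the AE wording on worsening of pre-existing conditions and the separate severity grade. Because the hold, discontinuation and suspension rules also refer to SAEs, a wider definition would widen their reach as now worded. Whether they apply to the added events is for the sponsor to decide and state.

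The cost is one amended sentence, the reconciliation of the dependent text, an occasional extra expedited report and, under the present wording, a possible temporary enrolment hold while an event is reviewed. No change to sample size, visits or analysis is needed.

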
Supplementary materials:

1. Intake Sheet

Oxidative Stress Markers in Inherited Homocystinuria and the Impact of Taurine Intake Sheet

Subject Name: _____ Date: _____

Characteristic	Comment
Sex	
Age	
BMI	
Salicylate intake over last two weeks	
Vitamin intake over last two weeks	
Supplement intake over last two weeks (taurine)	
Viagra intake over last two week/possible use over next 6 days	
Smoking habits	
Hypertension	
Diabetes	

Other chronic disease Infection Hormone replacement use Pregnancy Physical activity Diet prescription/compliance Medications/compliance (list all medications and dosing_)	
---	--

Reviewed by PI or co-investigator on: _____
 Proceed for nitroglycerin induced FMD YES/NO*
 Proceed for platelet studies YES/NO*
 *circle appropriate

			Comments (to include any limitations of activity)
System	Yes	No	
General/Constitutional			
general state of health			
sense of well being			
fever			
other			
Skin			
rash			
moisture/dryness			
other			
HEENT			
headaches			
vision			
hearing			
other			
Cardiovascular			
palpitations			
syncope			
other			
Respiratory			
difficulty breathing			
wheezing			
cough			
other			
Gastrointestinal			
appetite			
abdominal pain			
heartburn			
diarrhea			

	nausea			
	other			
Musculoskeletal				
	pain			
	cramps			
	other			
Genitourinary				
	dysuria			
	other			
Neurologic/Psychiatric				
	seizures			
	muscular coordination			
	emotional mood			
	other			
Allergic/Immunologic				
	reactions to drugs/foods			
	other			

II. Adverse Event Sheet:

Oxidative Stress Markers in Inherited Homocystinuria and the Impact of Taurine
 Adverse Event/Compliance Sheet

Subject Name: _____ Date: _____ Taurine intake:

System	Yes	No	Comments
General/Constitutional			
general state of health			
sense of well being			
Fever			
Other			
Skin			
Rash			
moisture/dryness			
Other			
HEENT			
Headaches			
Vision			
Hearing			
Other			

Cardiovascular				
	Palpitations			
	Syncope			
	Other			
Respiratory				
	difficulty breathing			
	Wheezing			
	Cough			
	Other			
Gastrointestinal				
	Appetite			
	abdominal pain			
	Heartburn			
	Diarrhea			
	Nausea			
	Other			
Musculoskeletal				
	Pain			
	Cramps			
	Other			
Genitourinary				
	Dysuria			
	Other			
Neurologic/Psychiatric				
	Seizures			
	muscular coordination			

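### Adverse-event severity is graded only by limitation of activity, so laboratory and blood-pressure events that limit no activity are Mild at any size, and the post-dose symptom sheet does not ask about limitation

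*Combined protocol and SAP*

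**What the plan says.** Section 8.B first says what counts as an adverse event: "Clinically significant changes in blood pressure or safety monitoring labs will be considered an AE". It then gives cut-offs, namely "liver function results that exceed two times the upper limit of normal, triglycerides greater than 400 mg/dl, and/or hypotension", which apply where the subject's values were normal before taurine. Each parameter has one cut-off, with no bands beyond it.

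For grading, the PI and one co-investigating physician "will determine the severity of the event and if the SAE or AE is related to the protocol using the categories noted below". The severity table that follows has three levels:

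- Mild: "No limitation of usual activities"
- Moderate: "Some limitation of usual activities"
- Severe: "Inability to carry out activities"

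No other severity scale appears in the document. The Safety Officers review the assigned grade, and where opinions differ the higher one stands.

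Two symptom forms are in the supplementary materials. The review-of-systems table printed before the heading of the Adverse Event Sheet, apparently part of the Intake Sheet, has a column headed "Comments (to include any limitations of activity". On the Adverse Event/Compliance Sheet the columns are Yes, No and a plain Comments column. The schedule in section 5.H marks the Intake Sheet for Day 1 only. It marks the Adverse Event/Compliance Sheet for 8 AM on Day 2 and on Day 6, and a footnote adds a telephone survey after the study.

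**The concern.** An activity-based scale suits symptoms. It has nothing to measure in an abnormal laboratory value or blood-pressure reading that the subject does not feel. Because the protocol makes such values adverse events and then requires this scale for all events, the rule gives a definite but uninformative answer for them. The plan is not silent on the matter.

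For symptoms the scale is suitable, but its input is not requested where it is needed. Grading a post-dose symptom requires knowing whether it limited activity. Deciding whether a symptom present before taurine has worsened requires comparing its intensity before and after. Section 8.B relies on that comparison twice: an exacerbation of a pre-existing condition counts as an adverse event, and the Not Related category turns partly on the intensity of a finding already present before exposure.

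What is at stake is the quality of the severity record. About 16 subjects will be exposed, the Safety Officers look at compiled data before children are recruited, and section 5.A says the pilot will be the basis for a later four-year study.

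**Working it through.** There is no stated figure to reproduce. The check applies the severity table literally and compares the two forms.

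**1. The scale applied to events that section 8.B defines.** The values are illustrative. Each laboratory value lies above its cut-off, and the subject is assumed to have been normal before taurine.

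| Event | Limits activity? | Grade under the table |
|---|---|---|
| Liver test 2.1 times the upper limit | No | Mild |
| Liver test 20 times the upper limit | No | Mild |
| Triglycerides 401 mg/dl | No | Mild |
| Triglycerides 1200 mg/dl | No | Mild |
| Hypotension below the cut-off, no symptoms | No | Mild |
| Hypotension with symptoms that limit activity | Yes | Moderate or Severe |
| Headache that prevents activities | Yes | Severe |

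The liver values differ by a factor of 20 / 2.1 = 9.5 and the triglyceride values by 1200 / 401 = 3.0, yet the grade does not change within either pair. This follows from the wording of the rule and is not an estimate of how often it will happen. The rule that the higher grade stands does not alter the result, because two raters who both follow the table both reach Mild.

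For context, exclusion criterion 10 in section 5.E remarks that "acute health care risk is generally seen in the setting of triglycerides > 1000 mg/dl". The protocol therefore recognises that the size of a triglyceride value matters, but the severity table does not use it.

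**2. Items on the Adverse Event/Compliance Sheet.** Leaving out the lines for other, the named items are: general 3, skin 2, head and senses 3, cardiovascular 2, respiratory 3, gastrointestinal 5, musculoskeletal 2, genitourinary 1, neurologic/psychiatric 3, allergic 1. The sum is 3 + 2 + 3 + 2 + 3 + 5 + 2 + 1 + 3 + 1 = 25. None has a prompt for severity or activity limitation.

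**3. Forms against the schedule.** The prompted table goes with the Day 1 form, before any taurine has been given. The unprompted sheet is the one marked at Day 2 before dosing and at Day 6. As scheduled, the prompt appears only when no treatment-emergent event can exist.

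**4. Where the grade is used.** Seriousness in section 8.B depends on outcome (death, hospitalization). Reporting and suspension in 8.B and the stopping criteria in 8.C depend on possible relatedness of a serious event, numeric cut-offs, a count of two or more subjects, and clinical judgement of laboratory changes. None refers to Mild, Moderate or Severe. Section 5.K plans no safety analysis by grade. The places affected are the severity entry for each event, the Safety Officers' review of that entry, and the intensity comparison within the relatedness categories.

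**The case against.** The strongest reply is that no safety decision depends on the grade. Laboratory data are reviewed within five working days of a subject finishing, abnormal results go to the physician co-investigators within five working days, and suspension follows from cut-offs, counts and clinical judgement. A liver test at 20 times the upper limit would be seen as a number, whatever word is attached to it. This stands, and it is why the point is minor. A reader might infer that an extreme value would escape the safety rules; the documents do not support that.

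A reader might also infer that every laboratory or blood-pressure event comes out Mild however extreme. That goes too far. An event that limits activity can be graded Moderate or Severe, and one that leads to hospitalization as section 8.B describes is a serious event regardless of grade.

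On the form, it is fair to say that the sheet has a Comments column, that study staff administer it, and that section 8.A provides for direct questioning at the last dose. Activity limitation and worsening can therefore be recorded, so the inference that a worsening symptom cannot be captured fails. What remains is that nothing on the sheet asks for either. Section 8.A also cites both sheets together for the questionnaires before and after dosing, so use of the unprompted sheet alone after dosing is what the schedule shows but is not beyond doubt.

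Lastly, the remark about triglycerides above 1000 mg/dl explains an exclusion cut-off. It is not a severity band that the protocol set and then ignored.

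**Conclusion.** The point holds in a limited form and is minor. Under section 8.B as written, a protocol-defined laboratory or blood-pressure event that does not limit activity is graded Mild at any magnitude, and the symptom sheet scheduled after dosing does not request the information on which the scale depends. The consequence is confined to the severity record, the Safety Officers' review of grades, and the before/after comparison used for relatedness. Stopping, suspension and expedited reporting are unaffected.

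This rests on two readings. One is that the severity table applies to all events, which is what the text says. The other is that the prompted review-of-systems table belongs to the Intake Sheet, which is inferred from its position ahead of the Adverse Event Sheet heading in text extracted from a PDF. If the second reading is wrong, the conclusion about the scale is unchanged; only the contrast between the forms would need to be restated.

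**What to change.** In section 8.B, state that the activity scale applies to symptomatic events, that laboratory and blood-pressure adverse events are graded by size of departure on a published toxicity scale named in the protocol, and that the higher grade is used when both apply.

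On the Adverse Event/Compliance Sheet, replace the plain Comments heading with the one already used on the preceding table, "Comments (to include any limitations of activity" (closing the bracket). For each item ticked Yes after dosing, add a yes/no entry for whether it is worse than before the first dose. Keep the meaning of Yes the same at every time point. Redefining it as new or worse on later sheets only would make the same box mean different things before and after dosing, and a persisting unchanged symptom would look the same as a resolved one.

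The cost is a short addition to section 8.B, a changed column heading and one further entry on the form. No extra samples or visits are needed. Some laboratory events will be reported at a higher grade than under the present table. Since no stopping or suspension rule uses the grade, that alone triggers nothing.
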